5.2.1 Dose Selection for MK-8962 and Dose Modification for hCG

5.2.1.1 Dose Selection (Preparation)

The rationale for dose selection of MK-8962 to be used in this trial is provided in Section 4.0 – Background & Rationale. Subjects with body weight ≤ 60 kg will be given MK-8962 100 μg and subjects with body weight > 60 kg will be given MK-8962 150 μg .

During the course of the trial, for subjects receiving MK-8962 100 μg , the dose of MK-8962 should be adjusted to 150 μg if the subject's body weight increases by 2 kg or more from the previous visit to a value greater than 60 kg. For subjects receiving MK-8962 150 μg , the dose should not be down-titrated for the rest of the trial regardless of any changes in body weight.

5.2.1.2 Dose Titration for hCG

The dose of hCG can be adjusted between 500 IU and 5,000 IU (inclusive) in order to keep the Total T and E2 levels within the normal ranges as defined in the paragraph below. As specified in the flow chart (Section 6.0), blood samples collected at Visit 9/Week 12 and each of the subsequent visits will be evaluated for the Total T and E2 levels. Based on the results of these tests, the investigator or qualified designee should log into the Interactive Voice/Web Response System (IVRS/IWRS) between pre-specified visits to request additional medication if hCG up-titration is needed. Note: A dose of hCG outside of this

range may be appropriate in certain subjects, based on the subject's Total T and/or E2 levels and/or any clinically relevant signs or symptoms (e.g., gynecomastia, breast pain, and/or tenderness), and will require prior consultation with the Sponsor.

The normal range for Total T for this study is defined as the mean \pm 2 standard deviation (SD) for a young, healthy male population, and the exact limits are assay-specific. The reference range used by the Sponsor-designated central lab is 240.00 – 950.00 ng/dL (or 8.3 – 33.0 nmol/L). During hCG treatment, serum E2 levels should also be evaluated to avoid clinically relevant elevations of E2 levels (should be monitored towards maintaining <40% above the upper limit of normal in men [the ULN from the Sponsor-designated central laboratory is 40.00 pg/mL]).

5.2.2 Timing of Dose Administration

MK-8962

Throughout the 64-week treatment period, a single dose of MK-8962 100 μ g (body weight \leq 60 kg) or 150 μ g (body weight $>$ 60 kg) is to be administered subcutaneously in the abdominal wall once every two weeks in the morning on the same day of the week throughout the trial. The fixed day of the week is chosen by the subject depending on individual preference. For the convenience of visit scheduling, a weekday injection is preferred, as most protocol-specified site visits fall on the same day of a scheduled MK-8962 administration. The time and dose of MK-8962 administration should be recorded in a paper diary.

Note: The subject should adhere to the same MK-8962 injection schedule (e.g., on every other Monday, etc.) throughout the trial, whenever possible. In the event that the subject misses a dose on a scheduled dosing day (e.g., a holiday, etc.), the make-up dose should be administered as soon as possible, and can only be administered within one week immediately following the missed dose. Otherwise, the missed dose should be skipped and the subject should continue on with the next regularly scheduled injection.

hCG

Starting from the last day of Week 12 (Day 85), hCG is to be injected twice a week in the morning, on fixed days of the week throughout the trial. The scheduling of hCG injection should be coordinated with the MK-8962 injection, as illustrated in [Table 3](#) below. After addition of the solvent to the freeze-dried substance, the reconstituted hCG solution should be administered by subcutaneous injection. The time and dose of hCG administration should be recorded in a paper diary. Note that [Table 3](#) is meant for illustration only, and the subject, in consultation with the investigator, may utilize any schedule that meets dosing interval requirements for hCG and MK-8962.

Note: The subject should adhere to the same twice-weekly injection schedule throughout the trial. In the event that the subject misses a scheduled hCG dose, the make-up dose should be administered as soon as possible, up to the day before the next scheduled injection day. This instruction for the handling of a missing hCG dose should be followed whether or not the subject also misses the MK-8962 dose at the same time.

Table 3 MK-8962 and hCG Dosing Schedule

Examples of Dosing Schedule Scenario	MK-8962 100 µg or 150 µg	hCG ^a
A	Every other Monday	Every Monday and Thursday
B	Every other Tuesday	Every Tuesday and Friday
C	Every other Wednesday	Every Wednesday and Saturday
D	Every other Thursday	Every Thursday and Monday
E	Every other Friday	Every Friday and Tuesday

^a The dose of hCG may be titrated between 500 IU and 5000 IU twice weekly to keep the Total T and E2 levels within acceptable ranges. A dose of hCG outside of this range may be appropriate in certain subjects, based on the subject's Total T and/or E2 levels and/or any clinically relevant signs or symptoms (e.g., gynecomastia, breast pain, and/or tenderness), and will require prior consultation with the Sponsor.

5.2.3 Trial Blinding/Masking

This is an open-label trial; therefore, the Sponsor, investigator and subject will know the treatment administered.

5.3 Randomization or Treatment Allocation

Dispensing of medication and assignment of screening and randomization numbers will be performed via the IVRS/IWRS. After signing informed consent, the investigator or qualified designee should enter the subject in the IVRS/IWRS and the system will assign a screening number. After evaluation of all screening data, indicating that the subject complies with all selection criteria, the subject can be assigned a randomization number to enter the MK-8962 priming phase. (Assignment of the randomization number should be done immediately prior to the initiation of MK-8962 treatment [i.e., on Day 1]).

Note: Even though the trial has an open-label, non-randomized design, a randomization number will be assigned per the Sponsor's standard procedure indicating the subject receives the trial medication. Therefore, in this protocol, the term randomization is equivalent to the term allocation.

5.4 Stratification

No stratification based on age, sex or other characteristics will be used in this trial.

5.5 Concomitant Medications/Vaccinations (Allowed & Prohibited)

Medications or vaccinations specifically prohibited in the exclusion criteria are not allowed during the ongoing trial. If there is a clinical indication for any medication or vaccination specifically prohibited during the trial, discontinuation from trial therapy or vaccination may be required. The investigator should discuss any questions regarding this with the Sponsor Clinical Director. The final decision on any supportive therapy or vaccination rests with the investigator and/or the subject's primary physician. However, the decision to continue the subject on trial therapy or vaccination schedule requires the mutual agreement of the investigator, the Sponsor and the subject.

5.6 Rescue Medications & Supportive Care

No rescue or supportive medications are specified to be used in this trial.

5.7 Diet/Activity/Other Considerations

Subjects do not need to adhere to any diet restrictions during the course of the trial. However, subjects should be counseled to refrain from excess intake of alcoholic beverages (>2 per day or binge drinking) and use of illicit substances during course of trial.

5.8 Subject Withdrawal/Discontinuation Criteria

A subject's consent may be withdrawn by the subject or the subject's legally acceptable representative (as appropriate) at any time for any reason or be dropped from the trial at the discretion of the investigator should any untoward effect occur. In addition, a subject may be withdrawn by the investigator or the Sponsor if enrollment into the trial is inappropriate, the trial plan is violated, or for administrative and/or other safety reasons. Specific details regarding discontinuation or withdrawal procedures; including specific details regarding withdrawal from Future Biomedical Research, are provided in Section 7.1.4 – Other Procedures.

Discontinuation from treatment is “permanent”. Once a subject is discontinued, he/she shall not be allowed to restart treatment.

A subject must be discontinued from the trial for any of the following reasons:

- The subject or legal representative (such as a parent or legal guardian) withdraws consent/assent.

A subject must be discontinued from treatment (but may continue to be monitored in the trial) for any of the following reasons:

- The subject develops an immediate or delayed study drug-related hypersensitivity reaction.
- The subject has neutralizing ADA against MK-8962.
- The subject, in the opinion of the investigator, persistently fails to comply with dosing, evaluation or other requirements of the trial.
- Any medical condition or personal circumstance which, in the opinion of the investigator, exposes the patient to risk by continuing with the study medication or does not allow the patient to adhere to the requirements of the protocol.
- The subject develops any condition for which corifollitropin alfa, or hCG is contraindicated in accordance with the local drug label of the country where the subject is participating.
- The subject has a serious drug-related adverse event

If a subject discontinues study medication (i.e., MK-8962 and hCG obtained through the study), he should complete all Discontinuation Visit procedures as described in Section 6.0. Please refer to Section 7.1.5.3 on how to manage patients who discontinue study medication but who do not withdraw consent.

5.9 Subject Replacement Strategy

A subject who discontinues from the trial will not be replaced.

5.10 Beginning and End of the Trial

The overall trial begins when the first subject signs the informed consent/assent form. The overall trial ends when the last subject completes the last study-related phone-call or visit, discontinues from the trial or is lost to follow-up (i.e. the subject is unable to be contacted by the investigator).

5.11 Clinical Criteria for Early Trial Termination

There are no pre-specified criteria for terminating the trial early.

6.0 TRIAL FLOW CHART

Trial Period:	MK-8962 Priming Phase															Combined Treatment Phase (MK-8962 / hCG) ^a																
	1	2	3	4	5	6	7	8		9	10		11		12		13		14		15		D/C ^b	Follow-up ^c								
Visit Number	1	2	3	4	5	6	7	8		9	10		11		12		13		14		15											
Visit/Contact Title:	Screening	Treatment Allocation								T C			TC		TC		TC		TC		TC			D/C ^b	Follow-up ^c							
Scheduled Week ^d :	-1	0	1	1	1	2	2	4	8	12	16	20	24	28	32	36	40	44	48	52	56	60	64 ^e									
Scheduled Study Day:	-7 to -1	1 ^f	3	5	8	11	15	29	57	85	113	141	169	197	225	253	281	309	337	365	393	421	449		+7 ^c							
Scheduling Window (Days):	-42 to -1								+/- 7	+/- 3	+/- 7	+/- 3	+/- 7	+/- 3	+/- 7	+/- 3	+/- 7	+/- 3	+/- 7	+/- 3	+/- 7	+/- 3	+/- 7	+/- 7	+/- 7	+/- 7	+/- 7	+/- 7	+24			
Administrative Procedures																																
Informed Consent and Assent ^g	X																															
Informed Consent and Assent for Future Biomedical Research ^h	X																															
Assignment of Screening Number ⁱ	X																															
Inclusion/Exclusion Criteria	X	X																														
Subject Identification Card	X																															
Medical History /Hypogonadotropic Hypogonadism History	X																															
Prior/Concomitant Medication Review ^j	X	X	X	X	X	X	X	X	X	X	X	X	X	X	X	X	X	X	X	X	X	X	X	X	X	X	X					
Assignment of Randomization Number		X																														
Diary Instructions		X								X																						
Dispense/collect Paper Diary		X							X	X	X	X	X	X	X	X	X	X	X	X	X	X	X	X	X	X	X					

Trial Period:		MK-8962 Priming Phase									Combined Treatment Phase (MK-8962 / hCG) ^a														
		1	2	3	4	5	6	7	8	9	10	11	12	13	14	15	D/C ^b	Follow-up ^c							
Visit Number	1	2	3	4	5	6	7	8	9	10	11	12	13	14	15										
Visit/Contact Title:	Screening	Treatment Allocation							TC		TC	TC	TC	TC	TC		D/C ^b	Follow-up ^c							
Scheduled Week ^d :	-1	0	1	1	1	2	2	4	8	12	16	20	24	28	32	36	40	44	48	52	56	60	64 ^e		
Scheduled Study Day:	-7 to -1	1 ^f	3	5	8	11	15	29	57	85	113	141	169	197	225	253	281	309	337	365	393	421	449		
Scheduling Window (Days):	-42 to -1								+/- 7	+/- 3	+/- 7	+/- 3	+/- 7	+/- 3	+/- 7	+/- 3	+/- 7	+/- 3	+/- 7	+/- 3	+/- 7	+/- 7	+/- 7	+24	
Review Diary to monitor compliance with Trial Medication									X	X	X	X	X	X	X	X	X	X	X	X	X	X	X		
Trial Medication																									
Dispense MK-8962 ^k		X				X	X		X	X		X		X		X		X		X		X			
Treatment with MK-8962			Once every two weeks (first dose on Day 1/Week 0 and last dose on Day 435 /Week 62)																						
Dispense hCG ^l									X	X		X		X		X		X		X		X			
Treatment with hCG											Twice weekly (e.g., every Monday and Thursday, or every Tuesday and Friday) ^m														
Clinical Procedures/Assessments																									
Full Physical Examination	X																						X	X	
Focused Physical Examination ⁿ		X								X							X								
Vital Signs (HR, BP measured twice)	X	X							X							X							X	X	
Weight (measured twice)	X	X					X	X		X	X		X		X			X		X		X	X		
Height for Growth Velocity (measured 3 times)	X	X							X						X								X	X	
Testicular ultrasound ^o	X	(X) ^t							X						X							X	X ^p	(X) ^p	
Tanner Staging ^q	X	X							X						X							X	X		
Adverse Events Monitoring	X	X	X	X	X	X	X	X	X	X	X	X	X	X	X	X	X	X	X	X	X	X	X		

Trial Period:		MK-8962 Priming Phase									Combined Treatment Phase (MK-8962 / hCG) ^a														
		1	2	3	4	5	6	7	8	9	10		11		12		13		14		15	D/C ^b	Follow-up ^c		
Visit Number																									
Visit/Contact Title:	Screening	Treatment Allocation								TC		TC		TC		TC		TC		TC		D/C ^b			
Scheduled Week ^d :	-1	0	1	1	1	2	2	4	8	12	16	20	24	28	32	36	40	44	48	52	56	60	64 ^e		
Scheduled Study Day:	-7 to -1	1 ^f	3	5	8	11	15	29	57	85	113	141	169	197	225	253	281	309	337	365	393	421	449		+7 ^c
Scheduling Window (Days):	-42 to -1								+/- 7	+/- 3	+/- 7	+/- 3	+/- 7	+/- 3	+/- 7	+/- 3	+/- 7	+/- 3	+/- 7	+/- 3	+/- 7	+/- 7	+/- 7	+/- 7	+24
Laboratory Procedures/Assessments																									
Serum for free T4	X																								
Hematology	X	X								X							X						X	X	
Chemistry Panel	X	X							X							X							X	X	
Serum for endocrine parameters ^r : FSH, LH, hCG, inhibin-B, AMH, Calc. Free T, and SHBG	X	X								X							X						X	X ^p	(X) ^p
Serum for endocrine parameters ^r : Total T and E2	X	X								X	X		X			X			X		X		X	X ^p	(X) ^p
Pharmacokinetic (PK) sampling for MK-8962 concentration ^s		see Section 7.1.3.3.1 Flow Chart for Pharmacokinetic Assessments																							
Sampling for Anti-MK-8962 antibodies ^r		X							X	X			X			X			X			X	X	X	

AMH = anti-Müllerian hormone; E2 = estradiol; FSH = follicle stimulating hormone; hCG = human chorionic gonadotropin; HIV = human immunodeficiency virus; LH = luteinizing hormone; SHBG = sex hormone-binding globulin; TC = telephone call; T = testosterone

^a The Combined Treatment Phase starts at the end of Week 12.

^b The Discontinuation (D/C) Visit is to be performed only if the subject does not complete the 64 week treatment. The D/C visit should be performed as soon as possible once the subject has prematurely stopped the study medication.

- c The post-treatment follow-up visit is to be scheduled at least 21 days (but no more than 45 days) after the last dose of MK-8962, and at least 7 days after the last dose of hCG (whether subject completed the trial or discontinued from the trial prematurely). Follow-up blood samples will be collected for assessment of anti-MK-8962 antibodies and PK for MK-8962 concentration. AEs and concomitant medication will also be assessed. For subjects wishing to continue on post-trial gonadotropin treatment, such treatment should not be started until after blood sample collection at this visit. For subjects who prematurely discontinue study medication, after the post-treatment follow-up visit, subjects who do not withdraw consent should: (1) return to the clinic for key visits (V9/Week 12, V12/Week 36 and/or V15/Week 64 as applicable) to have the following procedures performed: focus physical examination, vital signs, weight and height, Tanner staging, testicular ultrasound, laboratory assessment of endocrine parameters, and safety parameters (chemistry panel and hematology), and collection of concomitant medications and adverse events. Subjects discontinued from the treatment due to the presence of neutralizing ADAs will also have serum samples collected for ADA testing. Subjects who are unable or unwilling to return to the clinic at key visits will be contacted by phone to obtain adverse events and concomitant medications. (2) be contacted by phone in a timeframe similar to their original study visit schedule at visits that are not key visits, i.e., at V10, V11, V13, V14, up until the subject has reached Week 64 after V2, to assess for serious adverse events and concomitant medications. (3) Subjects discontinued from the treatment due to the presence of neutralizing antibodies may continue to be followed until the ADA result becomes negative or until clinically stable for up to 12 months after treatment discontinuation. Refer to Section 7.1.5.3 for further details.
- d For visits not involving PK sampling, a scheduling window of \pm 7 days is allowed.
- e No further injection of MK-8962 or hCG is administered at the Week 64 visit.
- f Day 1/Week 0 designates the first dose administration of MK-8962. The study medication is to be administered after completion of all Visit 2/Day 1 trial procedures (except for the collection of PK sample #02 which is to be performed 6-24 hours after the first MK-8962 injection). Visit 2 should be scheduled approximately 7 days after sample collection at Visit 1, when the central lab results are available to evaluate the Day 1 inclusion criteria.
- g Consent form must be signed prior to any study specific procedures; informed consent will be obtained from parent/legal guardian and assent (if applicable) will be obtained from subject.
- h Leftover main study serum from endocrine parameters, anti-MK-8962 antibodies, and PK for MK-8962 concentration will be stored at the end of the study for future biomedical research (FBR) if the subject consents to FBR. Eligible subjects will be able to participate in the main study even if they opt to not participate in FBR.
- i After obtaining the informed consent from the parent/legal guardian and the assent from the subject, the subject should be entered in the Interactive Voice/Web Response System (IVRS/IWRS) to obtain a screening number.
- j Any medication used from 30 days prior to screening through the end of the trial should be recorded.
- k Subject and his legal guardian (or someone designated by the subject's legal guardian such as a caregiver or parent) will be instructed at Visit 2 on home-administration of MK-8962 injections. The first 3 doses of MK-8962 will be administered by the subject at the site on Day 1, Week 2 and Week 4 as witnessed doses. Later injections can be self-administered by the subject or administered by the subject's legal guardian (or the designated person who has been appropriately trained) at home.
- l Subject and his legal guardian (or someone designated by the subject's legal guardian such as a caregiver or parent) will be instructed at Visit 9 on home-administration of hCG injections. The first dose of hCG will be administered by the subject at the site as a witnessed dose, and later injections can be self-administered by the subject or administered by the subject's legal guardian (or the designated person who has been appropriately trained) at home.
- m Treatment with hCG in combination with MK-8962 will start only if the subject has completed the 12-week MK-8962 priming phase.
- n The focused exam will include only heart, lungs, abdomen, extremities, and genitourinary exam.
- o At Visit 1/Screening, testicular ultrasound images will be read locally by the investigator (if qualified) or a local radiologist with appropriate training and expertise in reading testicular ultrasound. This local reader will calculate testicular volume to evaluate Inclusion Criterion #5, and evaluate the ultrasound for any presence of local pathology that would exclude the subject from participating (see Section 5.1.3 Subject Exclusion Criteria). In addition, all testicular ultrasound images will be sent to a central imaging vendor, and will be read in a masked manner after the subject completes participation in the study to assess study endpoints (i.e., testicular volume and sonographic pattern).
- p If testicular ultrasound or endocrine parameters is not able to be completed at study completion (V15) or on the day of D/C, the site should make an effort to schedule a visit within 4 weeks from the last dose of MK-8962 to perform these procedures. This visit can be combined with the post-treatment follow-up visit if it is scheduled at 21-28 days after the last dose of MK-8962. Testicular ultrasound does not need to be performed at D/C if this visit is \leq 6 weeks from the last scheduled testicular ultrasound measurement.

- ^q The investigator will use clinical assessment to assign the Tanner Stage for pubic hair and Tanner Stage for genital growth (e.g., penile length and scrotum development) separately, and perform a testicular ultrasound to measure testicular parameters as according to the procedures outlined in the Site Imaging Manual provided to the investigator site. The Tanner Stage for testicular volume will not be assessed clinically by the investigator and will be completed by the central imaging vendor according to the method described in the Independent Review Charter for imaging.
- ^r These blood sample collections should be performed prior to the injection(s) of MK-8962 or hCG, if there is any injection(s) scheduled for that day. Leftover main study serum will be stored at the end of the study for future biomedical research if the subject consents to future biomedical research.
- ^s A total of 13 PK samples are collected at various time points at Days 1 (2 time points), 3, 5, 8, 11, 29, 85, 169, 253, 337 and 449, as well as the follow-up visit. For details, see **Section 7.1.3.3.1 Flow Chart for Pharmacokinetic Assessments**. Leftover main study serum will be stored at the end of the study for future biomedical research if the subject consents to future biomedical research.
- ^t Testicular ultrasound is only to be performed at Visit 2 if the window is greater than 6 weeks between Visit 1 and Visit 2.

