5.2 Trial Treatment(s)

The treatments to be used in this trial are outlined below in [Table 2](#).

Table 2 Trial Treatment

Drug	Dose/Potency	Dose Frequency	Route of Administration	Regimen/Treatment Period/Vaccination Regimen	Use
MK-8962	Body weight ≤ 60 kg: 100 μ g Body weight >60 kg: 150 μ g	Once every two weeks	SC	Day 1 (Week 0) through Week 64. The last dose will be administered on the last day of Week 62 (Day 435).	Experimental
hCG ^a	500-5000 IU	Twice a week	SC	The first dose will be administered on the last day of Week 12 (Day 85), and treatment will be continued from Week 13 through Week 64.	Standard of care

^a Note: A dose of hCG outside of this range may be appropriate in certain subjects, based on the subject's Total T and/or E2 levels and/or any clinically relevant signs or symptoms (e.g., gynecomastia, breast pain, and/or tenderness), and will require prior consultation with the Sponsor.

The subject and his legal guardian (or someone designated by the subject's legal guardian such as a caregiver or parent) will receive instructions on MK-8962 and hCG home- injection prior to the initiation of treatment. The first 3 doses of MK-8962 will be self-administered or administered by the legal guardian (or a legal guardian-designated person who has been appropriately trained) at the trial site as witnessed doses at Visit 2 (Day 1/Week 0), Visit 7/Week 2 (Day 15), and Visit 8/Week 4 (Day 29). Note: The first dose of MK-8962 is to be administered after completion of all Visit 2/Day 1 trial procedures (except for the collection of PK sample #02 which is to be performed 6-24 hours after the first MK-8962 injection).

The first dose of hCG will be self-administered or administered by the legal guardian (or a legal guardian-designated person who has been appropriately trained) at the trial site as witnessed dose at Visit 9/Week 12 (Day 85).

The site should record in the source document when the instructions have been provided to the subject and his legal guardian (or someone designated by the subject's legal guardian such as a caregiver or parent) for home administration of MK-8962 and hCG.

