7.1.2 Clinical Procedures/Assessments

7.1.2.1 Physical Examination

A full physical examination will be performed at screening and at the end-of trial or discontinuation visit. Focused physical examinations will be performed during the trial, as specified in the Trial Flow Chart (Section 6.0). Focused physical examination will involve an examination for abnormalities of the heart/lungs, abdomen, extremities, and genitourinary exam. Only abnormal findings should be recorded on eCRFs, either as medical history (present at the screening visit) or as an adverse event (new findings during the trial). Refer to Section 7.2 for instructions on adverse event reporting.

These exams should be conducted by a licensed clinician (i.e., physician, physician's assistant, or nurse practitioner).

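### For boys who complete treatment, no scheduled examination covers the breast during the 52 weeks on hCG, although breast signs are named as possible grounds for an hCG dose outside 500-5000 IU

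*Combined protocol and SAP*

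**What the plan says.** **hCG dose.** Within the range, Section 5.2.1.2 ties titration to hormone levels: "The dose of hCG can be adjusted between 500 IU and 5,000 IU (inclusive) in order to keep the Total T and E2 levels" within their defined limits. It adds: "During hCG treatment, serum E2 levels should also be evaluated to avoid clinically relevant elevations of E2 levels". A separate note allows a dose outside the range on the basis of Total T and/or E2 and/or "any clinically relevant signs or symptoms (e.g., gynecomastia, breast pain, and/or tenderness), and will require prior consultation with the Sponsor". Footnotes to Table 2 and Table 3 repeat this note.

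**Examinations.** Section 7.1.2.1 places the full examination at the two ends of participation: "A full physical examination will be performed at screening and at the end-of trial or discontinuation visit". It does not list what the full examination contains. Between those points the examinations are focused. The flow chart (footnote n) says: "The focused exam will include only heart, lungs, abdomen, extremities, and genitourinary exam". Section 7.1.2.1 agrees: "Focused physical examination will involve an examination for abnormalities of the heart/lungs, abdomen, extremities, and genitourinary exam". Only abnormal findings go on the eCRF, as medical history or as adverse events.

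**Tanner staging.** Sections 7.1.2.4 and 12.6 cover pubic hair and genital development, with testicular volume read centrally. The breast is not part of it.

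**The concern.** The protocol names certain physical signs as capable of supporting a dosing decision, but the examination scheduled during hCG treatment is defined by a closed list that leaves that part of the body out. A site that follows the schedule to the letter would learn of gynecomastia or breast tenderness only if the boy mentions it, if someone happens to notice it, or if the investigator decides to look.

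Safety ascertainment is what is at stake. Evaluating safety and tolerability is one of the two primary objectives (Section 3.1), and adverse events are summarised by treatment phase (Section 8.6.2). Because only abnormal findings are recorded, an eCRF with no breast finding at Week 36 does not show whether the breast was normal or was not examined. The frequency of these signs in the combined phase could be understated, and their relation to E2 and hCG dose would be harder to describe. The primary efficacy estimate is not affected.

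**Working it through.** The plan states no figure to reproduce. The check sets the sections side by side and measures the interval from the scheduled study days.

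**1. What each scheduled assessment covers**

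| Assessment | Source | Breast covered? |
|---|---|---|
| Full examination: screening; V15 or discontinuation | 7.1.2.1, flow chart | Not stated; contents not itemised |
| Focused examination: V2, V9/Week 12, V12/Week 36 | Footnote n, 7.1.2.1 | No; five areas listed, closed by the word only |
| Tanner staging | 7.1.2.4, 12.6 | No |
| E2 and Total T: V9 and each later visit | 5.2.1.2, flow chart | No; laboratory values |
| Adverse-event monitoring at visits and calls | 2.1, 7.1.2.5, flow chart | No examination or breast question specified |
| Unscheduled procedures | 7.1 | At the investigator's discretion |

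The focused-examination row of the flow chart carries three marks. Its columns are displaced in the text available to me. Placing the marks at V2, V9 and V12 is my reading, supported by the key visits named in footnote c (Weeks 12, 36 and 64).

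**2. Length of the interval for a completer**

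- First hCG dose: Day 85, at V9 (Table 2).
- Next full examination: V15, Day 449.
- 449 - 85 = 364 days; 364 / 7 = 52 weeks.
- At two injections a week, 52 x 2 = about 104 injections. This measures exposure and does not count missed events.
- Footnote e: no injection is given at the Week 64 visit, so a finding made there cannot inform hCG dosing in the trial.

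**3. Where existing examinations fall**

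- V2 precedes hCG by 12 weeks. V9 is the day of the first hCG dose, so it can only serve as a baseline.
- V12 (Day 253) is the only one within hCG exposure.
- Day 85 to Day 253: 253 - 85 = 168 days = 24 weeks.
- Day 253 to Day 449: 449 - 253 = 196 days = 28 weeks.

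**4. Age of the baseline**

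Screening is about 1 week before Day 1, with a normal limit of 6 weeks (Section 7.1.5.1). If the full examination does include the breast, that finding is 1 + 12 = 13 to 6 + 12 = 18 weeks old when hCG starts.

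**5. Contacts between examinations**

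The flow chart schedules a visit or call every 4 weeks from Week 16 to Week 60: (60 - 16) / 4 + 1 = 12 contacts between Day 85 and Day 449.

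**6. Weight of one case**

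With about 15 boys enrolled, one unrecorded case moves an observed percentage by 1/15 = 6.7 points. At the enrolment cap of 35 (Section 8.9.1) it is 1/35 = 2.9 points. The documents give no basis for estimating how many cases would go unrecorded.

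**The case against.** The strongest reply is that the protocol already watches for the estrogen effect. E2 is measured at V9 and every later visit, with the aim of staying below 40% above an upper limit of 40 pg/mL, that is 40 x 1.4 = 56 pg/mL. There are 12 contacts with adverse-event monitoring during hCG. Pain and tenderness are symptoms, found by asking rather than by an examination list. Unscheduled procedures are allowed. Gynecomastia is neither an endpoint nor an event of clinical interest.

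Most of this stands, and it limits the point to partial under-ascertainment. It does not remove it. The hCG note joins hormone levels and clinical signs with and/or, so a sign may count on its own, and none of these routes asks anyone to look for or enquire about the breast.

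A reader might infer more than the documents support:

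- **That breast signs govern hCG titration.** They do not. They are examples attached only to doses outside 500-5000 IU with prior consultation; titration within the range uses Total T and E2.
- **That these signs go wholly unmonitored.** The routes above could pick them up.
- **That onset would be dated to the last visit.** Table 5 requires start and stop dates for each adverse event, so an onset the boy can recall would be recorded.
- **That the sections flatly contradict each other.** A note allowing action on a clinical sign can coexist with a limited scheduled examination. They are misaligned, and the closed list is what needs attention.
- **That boys who stop early are equally affected.** They have a full examination at the discontinuation visit, and trial hCG has then ended.

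**Conclusion.** The point holds in a limited form. For a boy who completes treatment, the 52 weeks on hCG contain no scheduled examination that covers the breast, and the first that might do so comes when hCG has ended. The other monitoring routes reduce the gap without closing it, so the frequency of these signs could be understated by an amount that cannot be estimated from the documents. It applies to every boy who enters the combined phase and completes it, out of about 15 enrolled, or up to 35 if enrolment is re-opened.

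The conclusion assumes that footnote n is read literally and that the focused examinations fall at V2, V9 and V12. Whether screening and V15 cover the breast is unknown, because the full examination is not itemised; if they do not, no scheduled examination in the trial does. This is an inexpensive improvement to safety data capture. It raises no question about which hCG dose or dosing rule is right.

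**What to change.** Reconcile footnote n and Section 7.1.2.1 with the hCG note in 5.2.1.2, Table 2 and Table 3, so that the signs the note names are recorded at focused examinations already scheduled. Week 12, done before the witnessed first hCG dose, would then give a current baseline, and Week 36 would give one observation on hCG. The same edit should state whether the full examination covers the breast, so that screening and V15 can be compared with them. The key visits after early stopping use the focused examination and would follow without further change.

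One examination on hCG still leaves intervals of 24 and 28 weeks. To cover these, include breast symptoms in the adverse-event enquiry already made at combined-phase visits and calls.

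The cost is a few wording changes and an added item at existing contacts, with no new visit, staff or equipment. The downside is that a few more mild findings will be recorded as adverse events. The change concerns what is recorded and proposes no dose or dosing rule.
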